#### **4.2.6.2 US FDA Primary Estimand Analysis**

For FDA estimand different strategies will be applied for ICEs of SCS rescue for NP and biologic use for NP (Section 4.1.3.2).

In Step 1 data collected after SCS rescue for NP will be utilised in the analysis. Data collected after biologic use for NP as well as after NP surgery will be set to missing for the purpose of imputation. Steps 2 and 3 will be repeated as described in Section 4.2.6.1. In Step 4, both post-surgery score and post-biologic for NP data will be replaced by WPS. The same ANCOVA model as described in Section 4.2.6.1 will be used for each imputed dataset. Rubin’s rule will be applied to combine analysis results (point estimates and standard errors) from the imputed datasets using PROC MIANALYZE. The results will be presented as shown in Section 4.2.6.1.

#### **4.2.6.3 Supplementary Estimand Analyses**

##### **4.2.6.3.1 Composite strategy for NP surgery, SCS/biologic for NP and IP discontinuation using WPS**

Supplementary analysis will be performed using different strategies (comparing to primary estimand) for SCS rescue for NP, biologic use for NP and treatment discontinuation.

In Step 1 data collected after NP surgery, SCS rescue for NP, biologic use for NP and treatment discontinuation will be set to missing. Steps 2 and 3 will be repeated. In Step 4, data after all 4 intercurrent events mentioned in Step 1 will be replaced by WPS. The same ANCOVA model as described in Section 4.2.6.1 will be used for each imputed dataset. Rubin's rule will be applied to combine analysis results (point estimates and standard errors) from the imputed datasets using PROC MIANALYZE. The results will be presented as shown in Section 4.2.6.1.

#### 4.2.6.3.2 Hypothetical strategy for COVID-19 infections

If more than 5% of participants in either treatment group have reported COVID-19 infections (based on the COVID-19 MedDRA terms), an additional supplementary analysis will be performed for the co-primary endpoints using a hypothetical strategy. Data after the first infection will be set to missing if NP surgery/SCS for NP/biologic for NP didn't occur prior to the COVID-19 infection. If COVID-19 infection started prior to the randomisation, data prior to the end date of the infection will also be set to missing. The analyses described in Section 4.2.6.1 will be repeated.

#### 4.2.6.4 Sensitivity Analyses

##### 4.2.6.4.1 Rank ANCOVA

To investigate the robustness of primary efficacy analyses for the co-primary endpoints, a rank ANCOVA model will be performed as described by [Stokes et al., 2000](#). More specifically, the ranks of post-baseline score and baseline score in the combined treatment group will be ranked using PROC RANK. The residuals from the linear regression of the response variable ranks vs ranks of the baseline score using PROC REG. The residuals in each treatment group will be compared using the CMH means score from PROC FREQ. The standardized transformed CMH statistic for the  $m$ th imputed dataset ( $st\_wh\_cmh^{(m)}$ ) will be calculated as follows and then combined using PROC MIANALYZE.

$$st\_wh\_cmh^{(m)} = \left( \sqrt[3]{\frac{cmh^{(m)}}{df}} - \left( 1 - \frac{2}{9 \times df} \right) \right) / \sqrt[2]{2/(9 \times df)}$$

where  $cmh^{(m)}$  is CMH statistic for the  $m$ th imputed dataset,  $df$  is the number of associated degrees of freedom ([O'Kelly and Ratitch, 2014](#)). The difference in median and 95% CI will be estimated using PROC QUANTREG (Mehrotra, 2017). The model will include the same covariates as in the ANCOVA model in Section 4.2.6.1. The median and standard error for each treatment group will also be estimated using PROC QUANTREG. The results from each MI dataset will be combined using PROC MIANALYZE.

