## 1.2 Study Design

This is a Phase 3, multicenter, randomised, double-blind, placebo-controlled, parallel-group, study to evaluate the efficacy and safety of repeat dosing of tezepelumab 210 mg SC versus placebo in participants with severe chronic rhinosinusitis with nasal polyposis (CRSwNP).

Approximately 400 participants will be randomised globally in a 1:1 ratio to receive tezepelumab 210 mg or matching placebo.

Participants will be stratified by region (China, Japan, and Rest of World [ROW]), prior nasal polyp surgery and co-morbid asthma/AERD/NSAID-ERD. Randomisation will be monitored to ensure that 50%-70% of the study population will have co-morbid asthma/AERD/NSAID-ERD, and at least 50% will have had prior surgery for CRSwNP. When the target percentage of participants in a stratum in a region is reached, consideration will be given to closing the IWRS randomisation for that subgroup, which may be done either overall or within a specific region. Once a subgroup is closed, participants in the screening/run-in period in the closed subgroup will not be allowed to be randomised and will be screen failed.

[figure not shown]
After enrolment, eligible participants will enter a screening/run in period and will have their current inhaled corticosteroid (INCS) therapy standardized to mometasone furoate nasal spray (MFNS) or equivalent INCS at Visit 1 and throughout the screening and study period.

Participants who continue to meet eligibility criteria will be randomised at Visit 3 (Day 0) to receive either placebo or tezepelumab 210 mg SC at randomisation (Week 0) and every 4 weeks thereafter (Weeks 4, 8, 12, 16, 20, 24, 28, 32, 36, 40, 44, 48). A total of 13 doses will be administered. An end of treatment (EOT) Visit will be conducted at Week 52.

The first approximate 200 randomised participants will have a 24-week follow up (FU) period without investigational product (IP) administration to assess durability of benefit. These participants will have the final safety assessment at Week 76. The remaining participants will be followed for 12 weeks after the end of treatment visit, with the final safety assessments at Week 64.

An overview of the study design is provided below in [Figure 1](#).

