**Step 4:** In the datasets from Step 3, replace post-surgery score with WPS, and replace post-SCS/biologic for NP score with WOCF. If a participant received both NP surgery and SCS for NP/biologic for NP, scores post-surgery will be set to WPS.

Each of the imputed datasets at Week 52 will be analysed using the analysis of covariance (ANCOVA) model with treatment group, baseline co-morbid asthma/AERD/NSAID-ERD status, prior surgery status, and region as factors (based on eCRF), and the baseline value as a covariate. Rubin’s rule will be applied to combine analysis results (point estimates and standard errors) from the imputed datasets using PROC MIANALYZE.

Descriptive statistics including number of participants, mean, standard error, and least squares (LS) means will be provided at Week 52. In addition, difference in LS means (using the observed marginal distribution of the sample covariates) and the corresponding 95% confidence intervals (CIs) will be provided along with the p-value. A single asterisk (\*) will be used to denote a result that is statistically significant at alpha = 0.05 and a double asterisk (\*\*) will be used to denote a result that is statistically significant at alpha = 0.01. Nominal p-values will be presented unless specified otherwise.

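### The rank ANCOVA p-value for the co-primaries adjusts for baseline rank only and leaves out the three randomisation factors; if those factors are prognostic the test is mildly conservative, and adding them costs almost nothing

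*SAP*

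**What the plan says.** SAP 4.2.6.4.1 describes the rank test in three steps:

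- Ranking: "the ranks of post-baseline score and baseline score in the combined treatment group will be ranked using PROC RANK".
- Adjustment: "The residuals from the linear regression of the response variable ranks vs ranks of the baseline score using PROC REG". Baseline rank is the only regressor.
- Test: "The residuals in each treatment group will be compared using the CMH means score from PROC FREQ". No stratification variable is named.

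The CMH statistic is then Wilson-Hilferty transformed in each imputed dataset and pooled with PROC MIANALYZE.

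The effect estimate shown with this test comes from another model: "The difference in median and 95% CI will be estimated using PROC QUANTREG". The sentence that follows is "The model will include the same covariates as in the ANCOVA model in Section 4.2.6.1". By its position it describes the quantile regression. The model it points to, in SAP 4.2.6.1, has "treatment group, baseline co-morbid asthma/AERD/NSAID-ERD status, prior surgery status, and region as factors (based on eCRF), and the baseline value as a covariate".

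On the design, SAP 1.2 says "Participants will be stratified by region (China, Japan, and Rest of World [ROW]), prior nasal polyp surgery and co-morbid asthma/AERD/NSAID-ERD". That makes 3 × 2 × 2 = 12 cells. Protocol 6.3 says randomisation is blocked but gives no block size.

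**The concern.** The p-value carries one covariate, while the interval beside it and the primary model carry four. The SAP gives no reason for the difference. The three missing factors are the ones on which randomisation was balanced.

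That balance matters for the variance. Stratified blocks remove most of the between-stratum variation from the treatment comparison. A test that ignores the strata still counts that variation in its denominator, so if the strata are prognostic its p-value is too large.

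This is the only rank-based test of the co-primaries, whose data will include worst-possible and carried-forward scores. If it came out weaker than the primary ANCOVA, a reader could not tell whether non-normality or the dropped factors caused the difference.

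**Working it through.** **1. The plan's own power figure.** The documents give no figure for the rank test, so the check starts from the stated design power (SAP 1.3): 200 per arm, two-sided 1%, at least 95% total power. With z = effect / (SD × √(2/200)):

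- NPS: 1.8 / (2.25 × 0.1) = 8.00. Less 2.576 this leaves 5.42, so power is above 99.9999%.
- NCS: 0.87 / (1.22 × 0.1) = 7.13. Less 2.576 this leaves 4.56, so power is 99.9997%.
- Joint power is at least the sum minus 1, or 99.9997%. The stated bound is met with a wide margin.

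**2. Expected size of the rank test as written.** Let D be the treatment-arm residual sum minus its expectation, S² the total residual variance, and R² the share of S² that the strata explain. The unstratified CMH statistic is D²/V with V = (n₁n₀/n) S². Under stratified blocks the true variance of D is about (n₁n₀/n)(1 − R²) S². Hence

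size ≈ 2{1 − Φ(1.96 / √(1 − R²))}.

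- R² = 0.05: 1.96/0.975 = 2.011, size 4.4%
- R² = 0.10: 1.96/0.949 = 2.066, size 3.9%
- R² = 0.20: 1.96/0.894 = 2.191, size 2.8%
- R² = 0.30: 1.96/0.837 = 2.343, size 1.9%

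**3. Simulation.** The null simulations had 400 participants in 12 strata and an NPS-like 0–8 score. These inputs are assumptions, because the documents do not give them:

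- blocks of 4;
- region shares of 15/10/75%;
- 65% with prior surgery and 60% with asthma;
- baseline correlation 0.4;
- R² from 0 to 0.30;
- complete data, with no pooling over imputations.

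The stratified comparator ranks within strata and uses a CMH test stratified on the 12 cells. The as-written column at 5% shows the range over separate runs.

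| Assumed R² | Size at 5%, as written | Size at 5%, stratified CMH | Size at 1%, as written | Size at 1%, stratified CMH |
|---|---|---|---|---|
| 0 | 4.97% | 4.70% | 1.07% | 1.02% |
| 0.05 | 4.4–4.7% | 4.78% | 0.65% | 0.77% |
| 0.10 | 3.9% | 4.77% | 0.55% | 0.87% |
| 0.20 | 3.2–3.4% | 5.28% | 0.58% | 1.20% |
| 0.30 | 2.1–2.3% | 4.92% | 0.28% | 0.97% |

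With 6,000 trials per setting, simulation error is about 0.3 points at 5% and 0.13 at 1%. The simulated sizes follow the formula. At high R² they lie a little above it, probably because incomplete blocks and the coarse score leave the strata a smaller share of the rank variance.

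**4. Factors in the regression step.** Adding the three factors to the rank regression gave sizes of 5.0%, 5.2% and 5.2% at R² = 0.10, 0.20 and 0.30. At R² = 0 it made no difference.

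**5. Power.** At a shift of 0.71 SD (NCS: 0.87/1.22), the as-written and stratified tests both rejected in 100% of 1,000 trials, at 5% and at 1%. A gap appears only for much smaller effects with strong strata. At 0.30 SD, R² = 0.20 and the 1% level, power is 72% as written against 79% stratified.

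**The case against.** The strongest case on the other side is that nothing depends on this p-value. The rank ANCOVA is listed as a sensitivity analysis, lies outside the testing hierarchy of SAP 4.1.2, and errs in the safe direction. That stands, and it limits the point to low severity.

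A reader might go further than the documents allow in four ways:

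- **That the test simply is conservative.** This holds only if the strata predict outcome beyond baseline rank. The documents give no figure for that. At R² = 0 there is no loss, and at R² = 0.05 it is close to simulation error.
- **That this is the only distribution-free check.** The quantile regression in the same section needs no normality and is adjusted. The NPS and NCS responder analyses (SAP 4.2.8.7 and 4.2.9.7) are covariate-adjusted and count surgery, SCS or biologic for NP as non-response. Only the narrower claim holds, that it is the only rank-based test.
- **That matching the covariates will make p-value and interval agree.** A mean-rank test and a median difference target different quantities and can disagree under identical adjustment.
- **That the simulated sizes are those of the SAP procedure.** The full procedure pools a transformed statistic over 100 imputations after worst-score and carried-forward replacement. The simulations cover the complete-data test only.

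It can also be said that the SAP cites a textbook for the method, and that CMH accepts strata, so stratification may have been intended. The documents cannot settle this. The steps written out omit strata, and two programmers could produce different p-values from the same text. That is reason enough for a clarifying sentence.

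**Conclusion.** The point holds as a low-severity inconsistency. As written, the rank ANCOVA p-value adjusts for baseline rank alone, while the primary ANCOVA and the accompanying median interval also adjust for the three randomisation factors.

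The consequence is conditional. Across assumed R² from 0.05 to 0.30, a nominal 5% test has a size of roughly 4.7% down to 2.1%, and with non-prognostic strata it keeps its nominal size. This rests on the assumed R², blocks of 4, the assumed stratum shares and complete data.

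The omission inflates no false-positive rate and changes no success decision. At the planned effects it does not alter the expected result of the rank test. A reader might infer that it weakens the co-primary conclusions, but the documents do not support that.

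**What to change.** In SAP 4.2.6.4.1, change the PROC REG step so that response ranks are regressed on baseline rank plus region, prior surgery status and co-morbid asthma/AERD/NSAID-ERD status. Use the eCRF values, as in 4.2.6.1, and say so, because SAP 4.2.2 summarises the factors from both IWRS and eCRF. Then compare the residuals by arm with the CMH mean score as now. The statistic keeps 1 degree of freedom, so the Wilson-Hilferty and MIANALYZE steps do not change.

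This is preferable to stratifying the CMH test on all 12 cells. With China and Japan as separate regions some cells may be sparse, and a stratified test would need a rule for them.

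The cost is one sentence and one MODEL statement, with no new data. SAP 2.1.4 rules out SAP updates after primary database lock. The change therefore belongs before lock; failing that, the CSR should state which factors each result adjusts for.

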#### 4.2.6.4.2 Control-based imputation

Control-based imputation (copy reference) will be performed to examine the robustness of the MAR assumption.

The analysis follows similar 4 steps as described in Section 4.2.6.1. Imputed dataset from step 2 in Section 4.2.6.1 will be used in step 3, where missing data from participants in the tezepelumab group who dropped out for treatment related reasons will be assumed missing not at random (MNAR) /dropout reason-based (DRMI) and will be imputed using the placebo group, whereas the remaining participants who dropped out will be imputed assuming MAR. Table 10 summarises how tezepelumab participants withdrawing from study will be handled in the DRMI analyses. A random seed of 539612 will be used. Step 4 will be repeated as in Section 4.2.6.1.

The same ANCOVA model as described in Section 4.2.6.1 will be used for each imputed datasets. Rubin's rule will be applied to combine analysis results (point estimates and standard errors) from the imputed datasets using PROC MIANALYZE. The results will be presented as shown in Section 4.2.6.1.

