- 1 The participant should be encouraged to return for all regular clinic visits and perform all scheduled assessments (excluding IP administration and, in the case of IP discontinuation due to NP surgery, nasal endoscopy and CT) until the EOT visit at Week 52 (+/-5 days).
- 2 The participant will be offered follow-up on a monthly basis via telephone calls while continuing ePRO data collection on the handheld device at home until the participant completes the EOT visit at Week 52 (+/-5 days). The UPSIT assessments will not be completed as per SoA at home after IPD visit until the participant returns to site at the EOT visit.
- 3 If the participant cannot or does not wish to comply with any of the options above, (or any component of them such as only telephone-based visits without completion of the eDiary), the Investigator will contact the participant at 52 weeks post-randomisation. No other study assessments will be performed prior to this contact.

The EOT visit will be completed immediately in the case of subsequent early withdrawal from option 1 or 2. Participants who do not wish to have any follow-up contacts will be discontinued from the study. All discontinued participants must return the eDiary at the EOT visit.

If the participant chooses option 1, all assessments will be completed as per the SoA as indicated in [Table 1](#). If the participant chooses option 2 or 3, the key information to be collected during the telephone calls are AEs/SAEs, changes in concomitant medication, health

care utilisation, and asthma exacerbation information (asthma/AERD/NSAID-ERD participants). Participants who initially choose options 1 or 2 and subsequently cannot or do not wish to comply with the requirements of their option can continue with a less intensive option (ie, participant initially choosing option 1 can continue with options 2 or 3, participants initially choosing option 2 can continue with option 3). Participant Withdrawal from the Study

A participant may withdraw from the study at any time at his/her own request or may be withdrawn at any time at the discretion of the investigator for safety, behavioural, compliance, or administrative reasons. This is expected to be uncommon.

A participant who considers withdrawing from the study must be informed by the Investigator about modified follow-up options (eg, telephone contact, a contact with a relative or treating physician, or information from medical records).

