**Figure 1 Study Design Schema**

Participants who prematurely discontinue IP will be encouraged to remain in the study and undergo appropriate study visits/procedures for the full 52-week planned treatment period, despite no longer receiving treatment. At the IP Discontinuation (IPD) visit the participant will be given the following 3 options (further details are given in the CSP Section 7.1.1):

1. The participant should be encouraged to return for all regular clinic visits and perform all scheduled assessments (excluding IP administration and, in the case of IP discontinuation due to NP surgery, nasal endoscopy and CT) until the EOT visit at Week 52 (+/-5 days).
2. The participant will be offered follow-up on a monthly basis via telephone calls while continuing ePRO data collection on the handheld device at home until the participant completes the EOT visit at Week 52 (+/-5 days). The UPSIT assessment will not be completed at home after IPD visit until the participant returns back to the site at the EOT visit.
3. If the participant cannot or does not wish to comply with any of the options above, (or any component of them such as only telephone-based visits without completion of the eDiary), the Investigator will contact the participant at 52 weeks post-randomisation. No other study assessments will be performed prior to this contact.

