## 4.2 Analysis Methods

### 4.2.1 Participant Disposition

Participant disposition will be summarised using the All participants analysis set. The number of enrolled participants will be summarised. The number and percentage of participants within each treatment group will be presented by the following categories; randomised, not randomised (and reason), received IP, did not receive IP (and reason), completed treatment, discontinued treatment (and reason), completed study (participants who completed IP and study, and participants who discontinued IP but completed study assessments), discontinued study (including reason), completed the short-term follow-up period, and completed the long-term follow-up period. Participant recruitment by country and centre will also be summarised.

The number and percentage of participants who discontinued IP, but remained in the study, will be presented by treatment group and option of follow up (Section 1.2).

Kaplan-Meier plots will be produced summarising the time (in days) to last dose of IP and premature withdrawal from the study separately. Participants without the premature event will be censored as described in Section 3.1.8.

The disposition due to the global/country situation will be summarized using the Randomised analysis set. The number and percentage of participants within each treatment group will be presented by the following categories: subjects who completed treatment, subjects who discontinued treatment due to the global/country situation, subjects who completed the study, and subjects who withdrew from the study due to the global/country situation. The global/country situation study disruptions will also be summarized for the Randomised analysis set. The number and percentage of participants within each treatment group will be presented by the following categories: participants with at least one disruption due to global/country situation (including type of disruption), and participants who discontinued treatment or withdrew from study due to global/country situation.

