**Table 10 Treatment arms for imputation of tezepelumab participants under DRMI**

Reason for withdrawing from study	Reason for discontinuing IP	DRMI
Site terminated by sponsor		Tezepelumab
Study terminated by sponsor		Tezepelumab
Death		Placebo
Loss to follow-up	Subject lost to follow-up	Placebo by default (pending blinded review of any further information)
Withdrawal by subject	Subject decision	Placebo by default (pending blinded review of any further information)
Other	Severe non-compliance to protocol	Placebo
	Adverse event	Placebo
	Development of study-specific discontinuation criteria	Placebo
	Pregnancy	Placebo
	Other	Placebo by default (pending blinded review of any further information)

A blinded review of subjects who discontinued IP for reasons of “Subject lost to follow-up”, “Subject decision” or “Other” will be performed prior to unblinding at the primary database lock. A listing of these subjects and the assumptions made under DRMI will be documented. If any recorded comments (on either of the “Discontinuation of Investigational Product” or “Disposition” eCRF pages) indicate clearly that the reason for study withdrawal was not related to treatment, then the “Placebo” default for DRMI in the above table may be changed for that subject.

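### The control-based sensitivity analysis assigns placebo imputation by study withdrawal, so tezepelumab participants who stop IP and take follow-up option 3 by default keep within-arm MAR imputation at Week 52

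*SAP*

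**What the plan says.** The primary analysis (SAP 4.2.6.1) fills missing values in Step 3 by regression within each treatment group, under MAR. The model holds baseline factors and scores at the visits, with no term for being off drug. Step 4 then overwrites scores that follow NP surgery, or SCS or a biologic for NP. For treatment discontinuation the primary estimand uses treatment policy (SAP 4.1.3.1), so the off-drug outcome is the target.

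The control-based analysis (SAP 4.2.6.4.2) alters Step 3: "missing data from participants in the tezepelumab group who dropped out for treatment related reasons will be assumed missing not at random" and are imputed from placebo, "whereas the remaining participants who dropped out will be imputed assuming MAR". For the assignment itself, "Table 10 summarises how tezepelumab participants withdrawing from study will be handled in the DRMI analyses". The first column of Table 10 is the reason for leaving the study; the reason for stopping IP is a second column. The placebo default may be lifted where eCRF comments "indicate clearly that the reason for study withdrawal was not related to treatment".

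Participants who stop IP choose one of three follow-up options (SAP 1.2; Protocol 7.1.1). Under option 3, "the Investigator will contact the participant at 52 weeks post-randomisation. No other study assessments will be performed prior to this contact". Option 3 is not withdrawal from the study. Protocol 7.1.1 says: "Participants who do not wish to have any follow-up contacts will be discontinued from the study". SAP 4.2.1 agrees: the number and percentage of "participants who discontinued IP, but remained in the study, will be presented by treatment group and option of follow up".

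**The concern.** Take two tezepelumab participants, neither with NP surgery nor with SCS or a biologic for NP. Both have their last dose at Week 12, both stop because of an adverse event, and both attend the IPD visit four weeks later. One leaves the study: withdrawal reason Other, IP reason adverse event, so Table 10 gives placebo imputation. The other takes option 3. There is no reason for study withdrawal, so no row is entered, and the missing Week 52 value stays with Step 3 of 4.2.6.1. Exposure, reason and missing data are the same, but the imputation differs because of an administrative choice.

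This analysis exists to test MAR, and within-arm MAR is least credible for someone who has been off drug for most of the year. Of the three sensitivity analyses, rank ANCOVA is not aimed at MAR and the tipping-point analysis is conditional. The control-based analysis is therefore the only unconditional test of MAR under the primary estimand. If it spares these participants, its support for robustness is somewhat overstated.

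**Working it through.** **1. The plan's own figure.** Inputs from Protocol 9.2: 200 per arm, effects 1.8 (NPS) and 0.87 (NCS), SDs 2.25 and 1.22, two-sided 1%. The standard error is SD × √(2/200) = SD × 0.1, that is 0.225 and 0.122. Effect over standard error is 8.0 and 7.1, against a critical value of 2.576. Power exceeds 99.99% for each endpoint and jointly, consistent with the stated figure of at least 95%. The point does not depend on this figure; it serves as the baseline for step 4.

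**2. Which option 3 participants lack a Week 52 NPS.** A last dose at Week w falls on day 7w + 1. The IPD visit is 28 days later (Protocol 7.1.1). Allowing ±5 days for the dose and ±5 for the visit gives a range of ±10. The NPS window for Week 52 is days 309-406 (SAP Table 2).

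| Last dose | IPD target day | Range | In days 309-406? |
|---|---|---|---|
| Week 12 | 113 | 103-123 | No |
| Week 36 | 281 | 271-291 | No |
| Week 40 | 309 | 299-319 | On target, yes, at the lower limit |
| Week 44 | 337 | 327-347 | Yes |

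The NPS gap therefore concerns last doses up to about Week 36. After Week 44, and after Week 40 if the visit is not early, the IPD endoscopy supplies the Week 52 value.

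**3. The same for NCS.** The Week 52 window is days 352-365 (SAP Table 3). Diary collection under option 3 ends with the IPD visit, which after a Week 44 dose comes no later than day 347. No last dose up to Week 44 gives a Week 52 NCS, so the gap is wider than for NPS.

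**4. Size.** Let f be the share of the tezepelumab arm that took option 3, was not rescued and has no Week 52 value. Moving that share from the full planned effect to a placebo-like outcome changes the mean difference by at most f × effect. The documents give no f, so a range is assumed.

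| f | Number of 200 | NPS shift | NCS shift |
|---|---|---|---|
| 1% | 2 | 0.018 | 0.009 |
| 2.5% | 5 | 0.045 | 0.022 |
| 5% | 10 | 0.09 | 0.044 |
| 10% | 20 | 0.18 | 0.087 |

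At f = 5% the effects become 1.71 and 0.827, which are 7.6 and 6.8 standard errors. Even at 10%, power at the two-sided 1% level stays above 99.99% under the design assumptions.

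**5. Where the 5% row comes from.** The tipping-point analysis (SAP 4.2.6.4.3) runs if more than 5% are missing at Week 52 in either arm. If it does not run, f cannot exceed 5%. If it runs, it shifts every MAR-imputed Week 52 value, including these.

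**The case against.** The strongest reply is that the rule is ambiguous rather than wrong. No sentence says that option 3 participants keep MAR, and the SAP does not define dropping out. The title of Table 10 is not limited to withdrawals, several of its rows differ only by IP reason, and the note below it begins "A blinded review of subjects who discontinued IP for reasons of" three listed reasons, with no condition that the person left the study. The sponsor may have intended assignment by IP reason. Moreover, SAP 4.2.1 counts an IP discontinuer as completing the study only if study assessments were completed, and SAP 3.1.8 treats any disposition status other than completed as premature withdrawal. An option 3 participant might thus be recorded as withdrawn and enter Table 10 after all.

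This stands as far as it goes: MAR is the default consequence of the text, not a stated rule. It does not remove the point. The sentence introducing the table, its first column and the override criterion all refer to study withdrawal, and both documents describe option 3 participants as still in the study.

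A reader might also infer that option 3 leaves no efficacy data before Week 52, or that these missing values are never stressed. The documents support neither. The IPD visit, due about four weeks after the last dose, includes endoscopy and patient-reported outcomes. The supplementary composite analysis (SAP 4.2.6.3.1) is unconditional and gives the worst possible score after IP discontinuation, which is harsher than placebo imputation, although it answers a different estimand. The tipping-point analysis also reaches them once its trigger is met.

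**Conclusion.** The point holds as a gap in one sensitivity analysis. As written, a tezepelumab participant who stopped IP, took option 3, had no prior NP surgery or SCS/biologic for NP and has no value in the Week 52 window is not reached by the placebo-imputation rule and keeps within-arm MAR by default.

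The bias favours tezepelumab and is small. When no tipping-point analysis runs, it is at most about 0.09 NPS points of 1.8 and 0.04 NCS points of 0.87. That bound assumes the planned effects and complete loss of benefit. The real shift should be smaller, because the imputation conditions on earlier scores and the within-arm donors include off-drug participants on options 1 and 2 who were seen at Week 52. Trial success is not threatened under the design assumptions. What is affected is how much support this analysis can lend to the MAR assumption.

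**What to change.** Before unblinding, amend SAP 4.2.6.4.2 and Table 10 as follows:

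- Assign imputation by the reason for IP discontinuation for every tezepelumab participant who discontinued IP and has a missing Week 52 value without prior NP surgery or SCS/biologic for NP, whether or not the participant formally withdrew.
- Use the reason for study withdrawal only where IP was not discontinued first.
- Apply the blinded review to these participants too, and let the override of the placebo default rest on the reason for IP discontinuation.

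Timing matters because SAP 2.1.4 rules out SAP updates after primary database lock. The cost is a few sentences, one changed condition in the imputation program and a somewhat longer blinded listing. The downside for the sponsor is that the control-based estimate may become slightly less favourable.
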